To date, studies of “early aggressive nutrition” in preterm infants have mainly focused on high protein intake to prevent protein catabolism.¹⁸⁻²¹ Nevertheless, provision of high protein intake without enough energy is unlikely to significantly reduce the early loss of protein and fat mass that had been accreted before birth. Early and high protein intake is currently a standard of care in our neonatal intensive care unit (NICU).

In summary, provision of high and early fat intake may help reducing the amount of postnatal weight loss. It may also help utilize the high amount of protein that is currently recommended to these premature babies. Also, we expect babies who get this appropriate intake to regain their birth weight earlier than others on slow fat increase regimen.

Methodology

Hypothesis:

We hypothesize that early higher fat intake in the first week after birth in VLBW infants results in less weight loss compared to the traditional provision of intravenous fat.

Study Design:

This is a randomized, non-blinded, controlled trial that will take place from March 2018 through February 2020 at the 39-bed level III NICU at Foothills Medical Center, Calgary, Alberta.

Intervention:

Starting Intravenous Lipid emulsions from D0 at 2 g/kg/day in the experimental group and increase to 3 g/kg/day the next day.

Comparison:

Control group: traditional start by 0.5-1 g/kg/day on D0 and increase daily by 0.5 g/kg/day till reaching 3 g/kg/day.

Outcome:

- Primary: The maximum percentage of weight loss in the acute stage of nutritional support: Defined as (birth weight–lowest postnatal weight)/birth weight× 100).
- Secondary:
 - Time to regain birth weight (day).
 - Time to reach 90 Kcal/kg/day (day).
 - Lipid tolerance: using serum TG levels (intolerance will be defined as TG> 2.8 mmol/L).
 - Incidence of EUGR at 36 weeks and at discharge.
 - Growth anthropometrics (weight, length and HC Z scores at 36 weeks and at discharge).
 - Incidence of ROP, BPD (28 days, 36 weeks CGA), brain injury and NEC.
 - Survival free major morbidity (BPD, ROP, NEC and severe IVH) at discharge.
 - Incidence of severe neurodevelopmental outcome at 18-22 months corrected gestation.
 - Length of stay.
 - Death.

Study Population:

a) Inclusion Criteria:

1. Preterm infants born with birth weight < 1500 g at Foothills Medical Centre (FMC)
2. Appropriate for gestational age (AGA) as per Fenton's growth charts
3. Anticipated duration of PN for >7 days

b) Exclusion Criteria:

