The investigators will conduct the randomization using a computer-generated allocation sequence (in random sized blocks for allocation concealment and balanced groups) generated at the University of Calgary. The lipid emulsions will be administered through an umbilical venous catheter, peripherally inserted central catheter, or peripheral line. The control group will begin treatment with 0.5 g/kg per day of 20% Intravenous Lipid Emulsion (IVLE) after birth if the birth weight is less or equal 1000g or 1 g/kg per day if birth weight is more than 1000g. The experimental group will begin treatment with 2 g/kg per day of 20% IVLE after birth. The IVLE dose in the control group will be increased by 0.5 g/kg per day daily until reaching 3 g/kg per day. The dose of IVLE will be increased directly from 2 to 3 g/kg per day the next day in the experimental group. Other macronutrients and micronutrients will be provided using the same products for amino acid and dextrose solutions in both groups. The maximum intake of amino acid will be 4 g/kg per day. The initial dextrose concentration in the parenteral nutrition (PN) will be 12.5%. The glucose infusion rate will be calculated and will be adjusted at the discretion of the attending neonatologist depending on the blood sugar levels. Total fluid intake will be started at 60 mL/kg per day for all infants. Monitoring for serum triglyceride will be performed after 24h of each lipid increment as per NICU policy in VLBW infants. This is part of routine care and not additional investigation. The serum triglyceride (TG) levels and other biochemical measurements such as serum electrolytes and acid-base status will be analyzed by the Calgary laboratory services at FMC. If hypertriglyceridemia occurs (>2.8 mmol/L, as per our current protocol), the IVLE concentration will be adjusted according to the following approved algorithm (Table 1).

Triglyceride Level (mmol/L)	Action
< 2.8	
 • Advance lipid intake as planned
2.8 – 4.5	
 • Reduce to previously tolerated dose
Greater than 4.5	
 • Stop lipid infusion for 24 hours

Table 1: Algorithm for adjusting IVLE in TPN.

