as the presence of a measured weight below the 10th percentile at the time of hospital discharge on Fenton's growth Charts. Hyperglycemia will be defined as glucose level >10 mmol/L. Two registered dietitians will calculate fluids, calories and protein intakes and record the day of life when the infants achieved 100 and 120 ml/kg per day and age when PICC line is removed.

Sample Size and Statistical Analyses:

The primary statistical analysis will be to determine the effect of higher rates of parenteral fat intake on the maximum percentage of postnatal weight loss of the VLBW infants, during the first week of life. Independent, 2-sample, *t* tests will be used to compare the two groups for this primary outcome. Our previous data showed a maximum percent of weight loss in VLBW infants of: 11.4 (SD= 5.2). Drenckpohl et al. found that the weight loss in the first week was 8% only in the experimental group of VLBW infants who received higher dose of IVLE.²² We considered 8% a reasonable percentage of weight loss in this category of infants and calculated our sample size to decrease our percentage by 3.4% (from 11.4% to 8%). Assuming an α value of 0.05 and a power of 0.80, a sample size of 76 infants (38 in each group) will be required.

Continuous variables such as days to achieve 90 kcal/kg per day, biochemical laboratory results, amount of lipid infused, and anthropometric results will be analyzed using independent, 2-sample *t* tests. Categorical variables such as hypertriglyceridemia, proportions of EUGR infants, IVH, BPD and ROP will be evaluated using Pearson χ^2 tests. All statistical tests will be 2-tailed, and the level of significance will be set at 0.05. All statistical analyses will be performed using STATA 11.1 (College Station, TX).

Feasibility and safety:

There are currently about 225 infants born at less than 1500 grams at FMC every year. With a 30% enrollment rate, the sample size will be reached in around 18 months. Halfway through enrollment, the overall rate of lipid intolerance will be reviewed. This will allow for a check for any unexplained sudden increase in incidence of lipid intolerance in relation to the study, or a significant reduction that may allow decreasing of the number needed to enroll. Neonatology section research assistant and study coordinator will help in recruiting and collecting the data.

Plans for dissemination or translation of results and plans for next steps in study of topic:

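### The half-way review lets the lipid intolerance rate lower enrolment, but the 76 infants were set by weight loss alone and leave nothing to cut

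*Combined protocol and SAP*

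**What the plan says.** The Outcome list names the primary outcome as "Primary: The maximum percentage of weight loss in the acute stage of nutritional support". Lipid tolerance is among the secondary outcomes, assessed "using serum TG levels (intolerance will be defined as TG> 2.8 mmol/L").

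Under Sample Size and Statistical Analyses, the calculation uses only the primary outcome: a fall from 11.4% (SD 5.2, from the unit's own data) to 8%, alpha 0.05 and power 0.80. All tests are two-tailed and the primary comparison is an independent two-sample t test. The result is that "a sample size of 76 infants (38 in each group) will be required". No allowance for dropout or death is stated.

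Feasibility and safety then adds an interim step: "Halfway through enrollment, the overall rate of lipid intolerance will be reviewed". It has two stated purposes. One is a "check for any unexplained sudden increase in incidence of lipid intolerance in relation to the study". The other is to detect "a significant reduction that may allow decreasing of the number needed to enroll". Intolerance is the only quantity under review in that sentence, so the reduction must be a reduction in intolerance. The plan gives no reference rate, threshold, size of cut, minimum enrolment or re-estimation formula.

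**The concern.** A sample size can sensibly be revised when new information bears on the quantities that fixed it. Here those are the difference in weight loss and its SD. The triglyceride-based intolerance rate is neither, so learning that it is low does not show that fewer infants suffice for the primary comparison. If the option were used, the trial could finish with less power than it promises, for a reason whose link to weight loss the plan does not set out. In a non-blinded trial, readers would also have no rule by which to understand why enrolment ended short. The plan intends a positive result to support routine use, and an underpowered null result could mislead the same decision.

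A smaller, separate point concerns the safety purpose. The review looks for an increase related to the study but uses the overall rate, which cannot attribute an excess to the experimental arm.

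**Working it through.** **Inputs**, from Sample Size and Statistical Analyses: difference 11.4 − 8 = 3.4 points; SD 5.2 in both arms; two-sided alpha 0.05; power 0.80; two-sample t test; equal arms. Standardised difference d = 3.4/5.2 = 0.654.

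**Reproducing the plan's figure.**
- Normal approximation: n per arm = 2 × [5.2 × (1.960 + 0.842)/3.4]² = 36.7, so 37 per arm (74 in total).
- Exact t test (noncentral t): n per arm = 37.7, so 38 per arm (76 in total). This matches the plan exactly.

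**Power at smaller sizes.** With arms n₁ and n₂, the noncentrality is 3.4/[5.2 × √(1/n₁ + 1/n₂)] and the degrees of freedom are n₁ + n₂ − 2. Power is the probability that the noncentral t statistic falls beyond the two-sided 5% critical value. At 76 the noncentrality is 3.4/[5.2 × √(2/38)] = 2.85 and the critical value is 1.993, giving power 0.803.

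The last column solves the same equation for the difference that gives 0.80 power with SD 5.2. The plan states no size of cut, so every total below 76 is an assumption.

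| Total infants | Power for 3.4 points | Difference needed for 0.80 power |
|---|---|---|
| 76 | 80.3% | 3.39 |
| 75 (38 + 37) | 79.8% | 3.41 |
| 74 | 79.2% | 3.43 |
| 68 | 75.7% | 3.59 |
| 60 | 70.2% | 3.83 |
| 50 | 62.0% | 4.21 |
| 38 (stop at the review) | 50.1% | 4.86 |

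**Is there reserve elsewhere?** None is stated. There is no dropout inflation, and twins and triplets go to the same arm with no allowance for clustering. Both are more likely to reduce power than to add to it.

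**Pooled intolerance rate.** The documents give no intolerance rates, so these are assumed. With equal arms the overall rate is the mean of the two arm rates:
- 20% and 20% by arm: (20 + 20)/2 = 20% overall.
- 10% and 30% by arm: (10 + 30)/2 = 20% overall.

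The two situations look identical. Against a 10% background, a 20-point excess confined to one arm appears as 20 − 10 = 10 points overall, half its true size.

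**The case against.** **The clause is only permissive.** It says a reduction may allow fewer infants, and the default stays at 76. That is true, and nothing shows how likely the option is to be used. But nothing elsewhere limits it or protects 76, and an undefined discretionary cut is harder to defend than a fixed rule.

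**The harm is to power, not validity, and small cuts cost little.** This stands. No type I error inflation or bias is claimed; losing one infant costs about half a percentage point of power and losing two about one point. The 50.1% figure is a worst case that requires stopping at the review itself. The difficulty is that the clause has no floor.

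**The normal approximation leaves some slack.** It does: 74 infants give 0.803 by that method, and 72 give 0.792. That is two infants, and the planned analysis is the t test, which leaves none.

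**Better tolerance could mean more lipid delivered and a larger effect.** This is the strongest substantive argument. Under the triglyceride algorithm in Study Protocol, fewer intolerant infants would mean fewer dose reductions, and delivered lipid is the trial's route to less weight loss. So intolerance is not wholly unconnected to the primary outcome. But the plan neither makes nor quantifies the argument: its assumed difference is 3.4 points whatever the intolerance rate, and the 8% target already comes from infants given higher-dose lipid. An overall rate also cannot show which arm tolerated lipid better, and better tolerance among controls would not enlarge the difference between arms.

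**The pooled rate may be enough for a safety check.** It can be compared with the unit's usual experience, each infant's triglycerides are already monitored and acted on, and the final analysis compares the arms on hypertriglyceridemia. This largely stands, so the by-arm table is only an optional improvement.

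**Conclusion.** The concern holds, and the clause allowing a smaller enrolment must be changed. It ties the only sample-size adaptation in the plan to a secondary outcome that had no part in setting 76. At the plan's own difference (3.4 points), SD (5.2) and two-sided alpha (0.05), 76 is the minimum for the planned t test, so any use of the clause leaves the primary comparison below 0.80. How far below depends on a cut the plan does not specify. Small cuts do little damage; the worst case is close to even odds of detecting the assumed effect. The conclusion would change only if a lower intolerance rate were shown to imply a larger weight-loss difference of the size tabulated, which the plan does not attempt. The by-arm point is minor and does not carry the same weight.

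**What to change.** In Feasibility and safety, delete the words that make a reduction in intolerance a ground for enrolling fewer infants, and add one sentence stating that 76 is not lowered on the lipid intolerance rate. Keep the half-way review for safety.

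Optionally, tabulate lipid intolerance by arm as well as overall at that review, as description only, with no efficacy or tolerance claim drawn from it.

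The cost is one clause removed, one sentence added and, if adopted, one small table from data already being collected. The study team gives up an option to enrol fewer infants for which the plan offers no basis. The table would add one descriptive between-arm look in a trial that is already non-blinded. No dose or clinical rule is affected.
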